6.0 Risks and Benefits

Risks

The following risks will be disclosed to all participants prior to obtaining their consent to participate:

- a) It is possible that participants may dislike the taste or texture of some of the thickened liquid stimuli in the study. Participants will be reminded that they are free to discontinue participation at any time.
- b) It is possible that participants may experience some fatigue during the data collection sessions. Participants will be reminded that they should disclose any fatigue or discomfort to the study personnel, and that they are free to discontinue any particular session or to withdraw from the study at any time.
- c) Participants will receive exposure to radiation during the videofluoroscopy. Based on our previous research, we estimate the total duration of exposure to be < 90 seconds, with an associated dose estimate of <0.27 milliSieverts. For comparison, a dose of 0.35mSv is reported by Moro and Cazzani (2006) to correspond to a risk of 1 in 39,000 of developing a radiation-induced stochastic effect from a videofluoroscopy. A study of videofluoroscopy radiation exposure in patients who completed an 11-task protocol showed that patients with neurological diagnoses received the highest exposure time (Mean: 3.1 minutes, 95% confidence interval: 2.9 to 3.2 minutes) (Bonilha et al., 2013). Extrapolating from this calculation to the 10-task protocol for the proposed study, we estimate that patients who complete the entire protocol could receive up to 3 minutes of radiation exposure. We will use a warning bell to alert the data collection team to exposure time above this limit, and will terminate the protocol at the first opportunity following the bell.
- d) Aspiration (entry of material into the airway) is a possible risk during the videofluoroscopic swallowing study that will be performed. This risk is always present for videofluoroscopic swallowing studies, which are intended to document the presence and severity of swallowing abnormalities, including (but not limited to aspiration). When aspiration is observed, standard procedures will be followed for documenting its occurrence. The protocol will be terminated immediately after the 4th observation of aspiration. Any participant who experiences aspiration will be provided with a “Summary of Research Findings” report that they can share with their family doctor. If appropriate, they will be referred to appropriate follow-up services.
- e) Participants may experience skin irritation due to the adhesive patches and medical tape used to attach the E-steth sensor to the neck. Individuals who report known skin sensitivity or allergies to adhesives will be given the option to decline the E-steth component of the study.

Benefits

Participants will benefit by receiving a comprehensive swallowing assessment that may not otherwise have been available to them.

Incidental Findings

In the unlikely event that the video x-ray reveals an unexpected medical finding, the team will generate a report and will facilitate referral to appropriate follow-up services.

7.0 Statistics

We will use the ASPEKT Method ([name] et al., 2019) to analyze available recordings of thin liquid, mildly thick liquid and extremely thick liquid swallows, and compare values to age matched reference data ([name] Swallowing Lab, 2019). Our goal is to develop an understanding of the prevalence of

abnormal values in PrC-19 taking comorbidities and other related factors into consideration. These potential covariate moderators include demographic factors (sex, age, gender, race, ethnicity), pre-existing or co-existing medical diagnoses, history of the COVID-19 hospitalization including details of any ventilator support required, medical history since discharge (including any occurrences of respiratory infection), dyspnea, changes in taste and/or smell associated with the COVID-19 infection, bulbar muscle strength, cough strength, and abnormal respiratory-swallow coordination. Additionally, the person's ability to tolerate the full range of diet textures and their swallowing-related quality of life may be affected by COVID-19 related swallowing difficulties.

Assuming 100 participants and 3 boluses per consistency, this will result in a dataset of 300 boluses per consistency. Our previous research suggests that swallowing can differ across repeated boluses of the same consistency within an individual. It is, therefore, reasonable to calculate statistical power at the bolus level. A power calculation in Study Size software suggests that a sample of 138 boluses for a given consistency will be needed to detect frequencies of abnormal values higher than those seen in the healthy reference sample with odds ratios ≥ 2.00 with 80% power. Therefore, the targeted sample size should be sufficient both to detect increased frequencies of abnormal values and to allow the bivariate exploration of the impact of single covariate moderators on abnormal value frequency. We will not have sufficient data to create a multivariate model exploring the relative impact of different moderators; however the findings from this analysis will be sufficient to inform future studies in larger cohorts.

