We will establish 3 regional research clinics that will offer comprehensive swallowing assessments to PrC-19 after initial recovery and a confirmed negative test for continuing COVID-19 infection. These research clinics will draw on established connections to clinicians in the Toronto area (PI [name]); the Hamilton-Niagara region to the west of Toronto (Co-I [name]) and in Gainesville, Florida (Co-I [name]). The assessments will include the collection of case history information, videofluoroscopy (i.e., a dynamic swallowing x-ray), use of a novel digital stethoscope to measure respiratory-swallow coordination, measures of other risk factors for dysphagia (e.g. bulbar muscle strength) and patient-reported outcomes. Detailed analyses of the videofluoroscopy swallowing studies (i.e. dynamic x-rays) will identify specific measures of swallowing that fall outside the range of normal variation based on comparison to healthy reference values established through our research program exploring swallowing physiology on liquids of different consistencies.

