3.2 Objectives

Our objective is to understand the nature of swallowing impairment in PrC19, based on the following outcome measures:

Primary Outcomes:

- Frequency of boluses (per consistency) on which the participant displays unsafe swallows defined as scores of 3 or higher on the Penetration-Aspiration Scale (Rosenbek et al., 1996)
- Frequency of boluses (per consistency) on which the participant displays inefficient swallows defined as swallows with pharyngeal residue measured to fill 1% or more of an anatomical reference scalar $[(C2-4)^2]$ on a lateral view x-ray ([name], 2020).

Secondary Outcomes:

- Frequency of boluses (per consistency) on which the participant displays time-to-laryngeal vestibule-closure more than 1 standard deviation above the healthy reference mean ([name] et al., 2019)
- Binary classification of a single pixel-based measure of pharyngeal area at rest, traced from a lateral view x-ray, and classified as below or above 1 standard deviation from the healthy reference mean ([name] et al., 2019)
- Frequency of boluses (per consistency) on which the participant displays pharyngeal area above the 75th percentile healthy reference value on the frame of maximum constriction ([name] et al., 2019)
- Frequency of boluses (per consistency) on which the participant displays multiple swallows, above the 75th percentile healthy reference value ([name] et al., 2019)

Exploratory Outcomes:

- Frequency of boluses (per consistency) on which post-swallow inspiration is seen immediately following the swallow.
- Maximum value across 3 repetitions of a maximum tongue-palate press using the Iowa Oral Performance Instrument in an anterior position.
- Range of diet textures included in the participant's diet, measured using the International Dysphagia Diet Standardisation Initiative Functional Diet Scale
- Total and individual question scores on the Sydney Swallow Questionnaire
- Reported dyspnea using the Modified Medical Research Council Dyspnea Scale
- Maximum peak voluntary cough flow across 3 repeated coughs through a peak-flow meter
- Patient report of any changes (Yes/No) they have experienced in taste or smell associated with their COVID-19 infection

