The x-ray procedure will involve swallowing 3 boluses each of thin, mildly thick and extremely thick barium and 1 consecutive drinking task of thin liquid.

Stimulus preparation: Bracco E-Z-Paque® powdered barium will be prepared in 20% w/v concentration with water, and thickened to target consistency using Resource Thicken-Up™ Clear (a xanthan gum thickener developed by Nestlé Health Science). Target consistency will be defined using the International Dysphagia Diet Standardisation Initiative definitions and Flow Test. For the Toronto site, all stimuli will be prepared in the Swallowing Rehabilitation Research Laboratory not longer than 6 hours prior to scheduled use, according to a strict standard operating procedure. Barium stimuli will be transported to the radiology suite at Toronto General Hospital, as per routine clinical procedures. Similar procedures will be followed at the Hamilton and Florida sites.

Procedure: Three cups of each stimulus will be prepared for the experiment, each containing 40 ml and organized in a muffin tray placed in front of the participant. If the participant completes all 3 thin sips without any observation of aspiration or serious residue, a new cup containing 90 ml of thin liquid will be provided, and the participant will be asked to drink the entire 90ml in a sequential fashion without stopping. This is a routine clinical method for ruling out swallowing safety concerns in patients who do not show concerns on single sip tasks. Single-use plastic teaspoons will be placed in the extremely thick cups to facilitate serving. The participant will be asked to take a

comfortable sip (or spoonful) from each cup. The cups will be weighed on a digital balance at the conclusion of the session to derive estimates of sip volume. The order of testing will begin with thin liquids and proceed to mildly thick and then extremely thick stimuli.

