5.0 Selection of Subjects

Participants

We aim to conduct 100 assessments (approx. 25 per collaborating site involved in the study and approx. 50 at University Health Network) over a 14-month period.

Recruitment

We will adopt three strategies for recruiting participants to this study:

1) We have linked to the Ontario COVID-19 Prospective Cohort Study (OnCoP) study being conducted by the CANCOV study PIs Drs. [name] and [name] at UHN. The CANCOV study team has agreed to notify their participants of the opportunity to participate in our study. They will use our

study information sheet and referral form for this purpose. They have also suggested that a Swallowing Team Member could attend their weekly clinic and speak directly to CANCOV participants who agree to consider the study.

2) We will work through the members of our clinician advisory group and a wider network of clinicians in the cities where data collection is happening to solicit referrals of patients who meet the study inclusion criteria. We will ask these clinicians to introduce the study opportunity to patients and request permission to complete a referral to the study team for future contact.

3) We will conduct a broad public advertising campaign through local newspapers, magazines, websites, mailings and posters at community centres, seniors' residences, places of worship, and around the university and hospital campuses of the study sites (University of Toronto, University Health Network Toronto, McMaster University, Hamilton Health Sciences Centre, University of Florida, Shands Medical Centre).

The clinical research coordinator will respond to all inquiries or referrals regarding potential participation, contacting the patient by phone or videoconference using Microsoft Teams to discuss the study further, obtain initial verbal consent and schedule the study appointments. A reminder call will take place 2 days before the scheduled study appointments.

Inclusion Criteria

- Adult (18 years of age or older)
- Positive (or presumed positive) diagnosis of COVID-19 infection not earlier than March 1, 2020
- At least 2 weeks post positive diagnosis and medical management of COVID-19 infection

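### Section 7.0 pools three sites and explores moderators one at a time without site, so a crude moderator odds ratio may partly reflect site differences

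*Combined protocol and SAP*

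**What the plan says.** The Introduction (2.0) describes a three-centre study: "We will establish 3 regional research clinics that will offer comprehensive swallowing assessments", in the Toronto area, Hamilton-Niagara and Gainesville, Florida. Section 5.0 sets the split at "approx. 25 per collaborating site involved in the study and approx. 50 at University Health Network".

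Section 7.0 then treats the data as one set of 300 boluses per consistency, to be compared with age-matched healthy reference data. The factors to be considered are given as follows: "These potential covariate moderators include demographic factors (sex, age, gender, race, ethnicity), pre-existing or co-existing medical diagnoses". The list goes on to hospital course and ventilator support, later medical history, dyspnea, taste and smell, tongue and cough strength, and respiratory-swallow coordination. Site is not named. The sample is judged large enough "to allow the bivariate exploration of the impact of single covariate moderators on abnormal value frequency", and the section adds: "We will not have sufficient data to create a multivariate model exploring the relative impact of different moderators".

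On how alike the sites are, Section 4.0 gives one barium product, one concentration, one thickener, one consistency standard and one acquisition rate (30 pulses and 30 frames per second). The place of preparation and the six-hour limit are stated for Toronto, followed by: "Similar procedures will be followed at the Hamilton and Florida sites". All data processing is done in Toronto. Section 5.0 lists three recruitment strategies: one works through a COVID-19 cohort study conducted at University Health Network, and the other two cover all study cities.

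**The concern.** Nothing in Section 7.0 would reveal a difference between sites or remove one. Three features leave room for such differences.

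- **Local delivery.** Stimuli are prepared and images acquired at each site. The set-up at Hamilton and Florida is not described beyond being similar.
- **Live decisions.** Under Section 4.0, testing of a consistency ends after a second observation of aspiration or serious residue, and the whole examination ends after a fourth aspiration. Staff make these calls during the examination, so they affect which boluses later reach central scoring.
- **Case mix.** One of the three recruitment routes is a cohort conducted at University Health Network; no counterpart is described for the other two sites.

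The moderator results are most exposed. If a site has both more abnormal swallows and more participants with a given factor, an unadjusted comparison credits the factor with what belongs to the site. The bias can go in either direction. Section 7.0 offers its findings as input to larger studies, so a misattributed association would carry forward.

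**Working it through.** **The plan's own figures.** 50 + 25 + 25 = 100 participants, and 100 × 3 = 300 boluses per consistency; both agree with the text. The 138 boluses quoted for an odds ratio of 2.00 at 80% power can be neither confirmed nor refuted, because the type I error, sidedness and reference rate are not given. (A two-sided two-sample test at an assumed 0.05 gives 141 per group at a reference rate of 30% and 137 at 50%.) The point below does not depend on that figure.

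**Inputs.** Site sizes 50/25/25 come from Section 5.0. The documents give no abnormal-swallow rate or moderator prevalence by site, so all rates below are assumptions. Site i has nᵢ participants, moderator prevalence mᵢ and abnormal rate rᵢ. The rate is the same with and without the moderator, so the true within-site odds ratio is 1.00 everywhere.

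**Formula.** With all sums over sites:

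crude OR = [Σnᵢmᵢrᵢ × Σnᵢ(1−mᵢ)(1−rᵢ)] / [Σnᵢmᵢ(1−rᵢ) × Σnᵢ(1−mᵢ)rᵢ]

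Three boluses per participant multiply every cell by 3 and leave the ratio unchanged.

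| Abnormal rate by site | Moderator prevalence by site | Moderator present: abnormal / normal | Moderator absent: abnormal / normal | Crude OR |
|---|---|---|---|---|
| 15/15/25% | 30/30/50% | 6.5 / 28.5 | 11 / 54 | 1.12 |
| 10/20/30% | 20/40/60% | 7.5 / 27.5 | 10 / 55 | 1.50 |
| 10/10/30% | 20/20/80% | 7.5 / 27.5 | 7.5 / 57.5 | 2.09 |
| 10/10/40% | 20/20/80% | 9.5 / 25.5 | 8 / 57 | 2.65 |
| 10/10/40% | 30/30/30% | equal rates in both groups | | 1.00 |
| 15/15/15% | 20/20/80% | equal rates in both groups | | 1.00 |

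The second row in full. Present: 10, 10 and 15 participants, with 1 + 2 + 4.5 = 7.5 abnormal. Absent: 40, 15 and 10 participants, with 4 + 3 + 3 = 10 abnormal. OR = (7.5/27.5)/(10/55) = 0.2727/0.1818 = 1.50.

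**Does stratifying remove it?** Mantel-Haenszel on the second row:

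- Numerator: (1×36)/50 + (2×12)/25 + (4.5×7)/25 = 0.72 + 0.96 + 1.26 = 2.94.
- Denominator: (9×4)/50 + (8×3)/25 + (10.5×3)/25 = 0.72 + 0.96 + 1.26 = 2.94.
- Ratio: 1.00, the true value.

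**Pooled frequency.** Assume a 10% reference rate and no true excess, with one 25-participant site reading at an odds ratio of 2 for measurement reasons alone. Its rate is 0.2222/1.2222 = 18.2%. The pooled rate is 0.75×10% + 0.25×18.2% = 12.0%, an apparent odds ratio of 1.23. If both collaborating sites read that way, the pooled rate is 14.1% and the apparent odds ratio 1.48. The documents give no evidence of such a shift; the figures show only what a by-site table would guard against.

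**How sparse are single sites?** With 25 participants and 20% carrying the moderator, there are 5 participants and 15 boluses per consistency. At a 10% rate that is 1.5 expected abnormal swallows.

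**The case against.** The best defence is that the design already limits site differences. Consistency target, materials and acquisition rate are specified once; preparation elsewhere is called similar; and both primary outcomes are measured centrally by one method. That stands, and it makes large scoring differences between sites unlikely. It does not deal with case mix, or with boluses never given because a live decision ended testing.

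A reader might infer that the sites differ in equipment, stimulus preparation and recruitment. The documents do not support this. No equipment difference is stated, preparation is described as similar, and two of the three recruitment routes are shared. A fair statement is that local conditions are not documented and not checked.

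A reader might also set a spurious odds ratio of about 2 against the plan's odds ratio of 2.00. That figure is for patients against the healthy reference sample. The plan sets no target for moderators, and the table needs a three- to fourfold gap in rate together with a fourfold gap in prevalence to reach it.

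Other points also carry weight. Moderator work is labelled exploratory. The list is open-ended, so site is unlisted rather than excluded. True case-mix differences belong to the population described and do not in themselves bias the pooled prevalence. These lower the severity but do not supply the missing check. The plan's statement that a multivariate model is out of reach is no obstacle: one moderator plus site is not a model of several competing moderators.

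**Conclusion.** The concern holds as a gap in the analysis, not as evidence that the sites differ. Three sites are pooled, moderators are examined singly and unadjusted, and site appears in neither the primary nor the moderator analysis. Under assumed rates and no within-site effect, the crude odds ratio ranges from about 1.1 for mild site differences to 2 or more for extreme ones, and is exactly 1.00 if either the rate or the prevalence is equal across sites. Which case applies cannot be known from the documents. Because scoring is central, stimulus targets are common and the moderator analyses are exploratory, this is a minor point and a cheap improvement.

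**What to change.** In Section 7.0:

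- Report each primary outcome, per consistency, by site as well as pooled. Label the by-site figures descriptive.
- Report each single-moderator odds ratio both crude and site-adjusted, by Mantel-Haenszel stratified by site or a model with the moderator and a two-degree-of-freedom site term. Either way, intervals should allow for boluses clustered within participant.
- Where the crude and the pooled site-adjusted estimates differ materially, state that the association may partly reflect site.
- Do not make detection within individual sites the criterion. With about 1.5 expected events in a cell, as in the example above, failure to see an association at one site says little, and such a rule would discard real effects.

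The cost is a few sentences. No new data are needed, since each site enrols its own participants and holds its own code key (Section 9.0). The downside is slightly wider intervals for the adjusted odds ratios and imprecise by-site estimates at about 25 participants each.

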Procedure	Participants will be asked to attend two 60 minute visits where we will capture a videofluoroscopy, measurement of respiratory-swallow coordination using a digital stethoscope, measures of tongue and cough strength and patient reported measures that will help us to understand the presence and impact of swallowing impairment (dysphagia) in this population. If requested, it may be possible to arrange for both visits to take place on the same day.
Primary Outcomes	
 • Frequency of boluses (per consistency) on which the participant displays unsafe swallows, defined as scores of 3 or higher on the Penetration-Aspiration Scale (Rosenbek et al., 1996). • Frequency of boluses (per consistency) on which the participant displays inefficient swallows, defined as swallows with pharyngeal residue measured to fill 1% or more of an anatomical reference scalar $[(C2-4)^2]$ on a lateral view x-ray.
Secondary Outcomes	
 • Frequency of boluses (per consistency) on which the participant displays time-to-laryngeal-vestibule-closure more than 1 standard deviation above the healthy reference mean ([name] et al., 2019). • Frequency of boluses (per consistency) on which the participant displays laryngeal-vestibule-closure duration more than 1 standard deviation below the healthy reference mean ([name] et al., 2019). • Pixel-based measurement of pharyngeal area at rest from a single a lateral view x-ray image, and classified as below or above 1

	
standard deviation from the healthy reference mean ([name] et al., 2019).
 
 • Frequency of boluses (per consistency) on which the participant displays pharyngeal area above the 75th percentile healthy reference value on the frame of maximum constriction ([name] et al., 2019). • Frequency of boluses (per consistency) on which the participant displays multiple swallows, above the 75th percentile healthy reference value ([name] et al., 2019).

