3.3 Hypothesis

Our current expectations are that PrC-19 will show differences in swallowing function and physiology compared to age- and sex-matched reference values ([name], 2019), as listed in the following table:

Parameter	Prediction in PrC-19 (vs age-matched healthy reference values)
Penetration-Aspiration	Higher frequency and more likely to be silent
Time-to-Laryngeal-Vestibule-Closure (LVC)	Later closure due to priority of respiration
LVC duration	Shorter due to underlying respiratory challenges
Pharyngeal Area at Rest	Larger due to muscle weakness and atrophy. Note: reference values show significant sex difference with larger area in males.
Pharyngeal Area at Maximum Constriction	Larger (i.e. poor constriction) due to muscle weakness and atrophy
Residue	Greater due to poor constriction
# of swallows per bolus	Higher due to poor bolus clearance

We expect PrC-19 patient to report swallowing-related burden. We hypothesize that post-swallow inspiration (a sign of respiratory-swallow discoordination) will be seen more commonly in PrC-19 compared to healthy reference data (Valenzano et al, 2020), and will be particularly common in those who report dyspnea.

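### Section 7 states the moderator analyses only on yes/no abnormal frequencies, although four per-bolus outcomes are measured on continuous scales; a measured-value analysis should be added beside them

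*Combined protocol and SAP*

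**What the plan says.** Section 7.0 sets a descriptive aim: "Our goal is to develop an understanding of the prevalence of" abnormal values, taking comorbidities and related factors into account. It lists many candidate moderators, including demographics, ventilator support, dyspnea, and tongue and cough strength. It rules out a multivariable model of their relative impact for lack of data. What remains is single-moderator work, and the sample is said to be enough "to allow the bivariate exploration of the impact of single covariate moderators on abnormal value frequency".

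Four outcomes counted this way are scaled measurements on each bolus, reduced to a flag:

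- Residue, a primary outcome: "pharyngeal residue measured to fill 1% or more of an anatomical reference scalar" (Section 3.2).
- Time to closure: "time-to-laryngeal-vestibule-closure more than 1 standard deviation above the healthy reference mean" (Protocol Summary; also in Section 3.2).
- Closure duration: "laryngeal-vestibule-closure duration more than 1 standard deviation below the healthy reference mean" (Protocol Summary; not in the Section 3.2 list).
- Constriction: "pharyngeal area above the 75th percentile healthy reference value on the frame of maximum constriction" (Section 3.2).

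Section 3.3 words its predictions for these measures as changes in size or timing, for example "Later closure due to priority of respiration", with shorter closure, larger constricted area and greater residue. Section 7.0 also says values will be compared with age-matched reference data. That sentence concerns the healthy reference, and no model relating measured values to moderators is given.

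**The concern.** The cut-offs suit the aim of reporting how often values are abnormal. A comparison of patients with one another (ventilated or not, dyspneic or not) does not have to pass through a cut-off. A flag treats a bolus with residue just over 1% the same as one with gross residue, and ignores all variation on either side of a timing or area threshold.

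Because the multivariable model is ruled out, the single-moderator analyses are the plan's only stated route to describing who is impaired, and Section 7.0 intends them to inform larger studies. If they rest on flags alone, a moderator that shifts these measures moderately may go unseen, and the null result would be carried forward.

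**Working it through.** **The plan's own figure.** Section 7.0 states 138 boluses per consistency for an odds ratio of at least 2.00 with 80% power, against the healthy reference. It gives no alpha, sidedness or reference rate, so 138 cannot be uniquely reproduced. With two-sided 5%, no continuity correction and p̄ = (p0 + p1)/2, the size per group is

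n = [1.96√(2p̄(1−p̄)) + 0.842√(p0(1−p0) + p1(1−p1))]² / (p1−p0)².

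This gives 137 at a reference rate of 1/3 or 1/2, 200 at 15.9% (1 SD, normal measure) and 152 at 25% (75th percentile). The figure concerns patients versus healthy adults. No moderator effect is stated anywhere, so using odds ratio 2 for a moderator below is an assumption.

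**Information kept by the flag.** Assume a normal measure and a moderator that shifts everyone with it equally. With odds ratio 2, p1 = 2p0/(1+p0), and the shift is z(1−p0) − z(1−p1).

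- 1 SD cut: p0 = 0.159, p1 = 0.274, shift 0.399 SD, p̄ = 0.216. Ratio = [(0.115/0.412)/0.399]² = 0.49.
- 75th percentile: p0 = 0.25, p1 = 0.40, shift 0.421 SD, p̄ = 0.325. Ratio = [(0.15/0.468)/0.421]² = 0.58.
- Small-shift limit, φ(z)²/[p0(1−p0)], with φ the normal density at the cut: 0.44 and 0.54.

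The flag therefore keeps 44 to 58% of the information and discards 42 to 56%. This is per bolus. Cutting also lowers the correlation between a participant's boluses (a latent ICC of 0.2 to 0.8 becomes 0.10 to 0.57), which returns part of the loss at participant level.

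**Power under a uniform shift.** Simulation of 100 participants with 3 boluses each, two-sided 5%, participant-level tests. Assumed: odds ratio 2, ICC 0.1 to 0.7, moderator present in 20 to 50 participants.

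- Welch test on the flag proportion versus rank test on the participant mean: gain of about 11 to 32 points. At ICC 0.3 and a 30/70 split, 43% versus 67% (1 SD) and 54% versus 73% (75th percentile).
- Rank test on both: gain of about 7 to 24 points. Part of the upper end above therefore comes from the Welch test in unequal groups.
- t-tests on both, ICC 0.2 to 0.8: about 8 to 23 points at odds ratio 2. Across odds ratios 1.5 to 3, and depending on how clustering is handled, about 1 to 30.
- Strongly right-skewed measures analysed as raw means: −3 to 8 points. A log transform restores the normal-case result.

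**Power when only a subset is impaired.** Keep the same abnormal rates, but let about 17% (1 SD) or 23% (75th percentile) of moderator-positive participants shift by 2 SD and the rest not at all. At ICC 0.3 and a 50/50 split, the Welch flag test has 47% against 29% for the rank test on means (1 SD), and 60% against 48% (75th percentile). Over the same ICC and split ranges the flag runs from 22 points better to about 5 worse.

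**Residue.** The documents give no distribution. Assuming a floor at zero (30 to 80% of boluses with none) and 10 to 40% above the cut, the uniform-shift gain is 4 to 26 points, smallest when most non-zero values already exceed 1%.

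**Raw values and age.** Assume no true moderator effect, 70% versus 40% older participants in the two groups, a 30/70 split and ICC 0.3. If age moves the norm by 0.5 SD, a rank test on raw values rejects 14% of the time; at 0.8 SD, about 26%. Age-referenced flags stay at 5 to 6%.

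**The case against.** The strongest case for the plan has four parts.

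- **The flags answer the plan's question.** The goal is prevalence of abnormal values and the outcomes are defined as frequencies. A shift within the normal range is a different question. This stands, and is why the frequency analyses should stay.
- **Matched referencing does real work.** Section 3.1 says the reference data allow age-related change to be accounted for, and Section 3.3 speaks of age- and sex-matched values. Raw milliseconds or percentages lose that, as the last calculation shows. This stands, and it shapes the fix.
- **The sentence about moderators justifies sample size; it does not specify a model.** A reader might infer that the plan forbids continuous analysis. It does not. It simply states no other scale for the moderators, and that gap is the point here.
- **The work is exploratory.** This limits the consequence. A reader might infer that real moderators will be missed; the documents support only that some could be, under a uniform shift. A second scale also adds tests: four measures by three consistencies is 12 per moderator, so 24 with both.

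**Conclusion.** The gap is real and modest. Moderator analyses are stated only on flags, while four of the outcomes are measured continuously and their predictions concern size or timing. Under a uniform shift in a roughly normal measure the cut discards 42 to 56% of the information. At an assumed odds ratio of 2, ICC 0.1 to 0.7 and a moderator in 20 to 50 of 100 participants, that is about 7 to 32 points of power, depending on the test.

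A reader might take such a range as what this plan loses. The documents do not support that. They give no moderator effect, split, ICC or distribution, their odds ratio of 2.00 belongs to the comparison with healthy adults, and under subset impairment the flag can match or beat the measured value. Nor do they support replacing the flags with raw values. Since neither scale is better in every case, the two belong side by side. The point does not touch pharyngeal area at rest, the Penetration-Aspiration Scale cut, or whether 1 SD is a fair definition of abnormal.

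**What to change.** Keep the abnormal-bolus frequencies and their moderator analyses. Add to Section 7.0, for residue, time to closure, closure duration and pharyngeal area at maximum constriction:

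- a moderator analysis, by consistency, of the measured per-bolus value expressed relative to the age- and sex-matched healthy reference (for example a z-score), or with age and sex as covariates;
- a mixed model with a participant random intercept, on a log or rank scale if skewed; for residue with many zeros, a rank test on participant means;
- both results reported side by side and labelled exploratory.

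Leave the Penetration-Aspiration Scale cut as it is.

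The cost is a few sentences and some analysis time. The flags are derived from the measured values, so no further participants, assessments or radiation are needed. The downsides are more exploratory tests and a second effect scale to report.
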